4.6.3. Laboratory Safety Variables

The clinical laboratory data consists of blood chemistry, hematology, and urinalysis.

Samples for laboratory testing will be collected at visits according to the Schedule of Events (Appendix 11.1). Samples will be analyzed by a central laboratory. The clinical laboratory data consists of blood chemistry, hematology, urinalysis and other specified in section 9.2.5 of the protocol.

Clinical laboratory values will be presented in Standard International (SI) units.

Potentially clinically significant value (PCSV) ranges will be applied to the laboratory test values as applicable (see PCSV criteria in Appendix 11.2).

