5.8.2. Clinical Laboratory Measurements

Laboratory test results will be tabulated by baseline and change from baseline to each scheduled assessment time with descriptive statistics.

Number and percentage of subjects with potentially clinically significant value (PCSV) at any post-randomization time point will be tabulated for each clinical laboratory test for all subjects and separately for subjects in whom the PCSV criterion was normal or missing at baseline.

Shift tables based on baseline normal/abnormal and other tabular and graphical methods may be used to present the results for laboratory tests of interest.

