6.3. Data Handling Convention for Missing Data

Adverse Event

If the severity of a TEAE is missing, it will be classified as severe in the frequency tables by intensity of TEAEs.

If the assessment of relationship of a TEAE to either Moderna mRNA-1273 vaccine or REGN10933+REGN10987 is missing, following rules will be applied

- If the relationship to Moderna mRNA-1273 vaccine is missing, the TEAE will be classified as related to Moderna mRNA-1273 vaccine if the TEAE occurs after the first dose of vaccine
- If the relationship to REGN10933+REGN10987 is missing, the TEAE will be classified as related to REGN10933+REGN10987 if the TEAE occurs after the REGN10933+REGN10987 administration

If the start time of an AE is completely missing, it will be assumed to have occurred on the time of the first dose of Moderna mRNA-1273 vaccine or REGN10933+REGN10987 (as applicable and whichever occurs first). When the partial AE time information does not indicate that in which period (pre-treatment/pre-vaccination/vaccination/post-vaccination) the AE starts, the following rules will be applied (1) if the AE could happen either in pre-treatment or pre-vaccination periods, the AE will be classified to the pre-vaccination period (applicable to arms 1, 2, 3, 4, 5, 7, 8); (2) if the AE could happen either in pre-treatment or vaccination periods, the AE will be classified to the vaccination period (applicable to arms 6a – 6d and 9); (3) if the AE could happen either in pre-vaccination or vaccination periods, the AE will be classified to the vaccination period (applicable to arms 1, 2, 3, 4, 5, 7, 8); (4) if the AE could happen either in vaccination or post-vaccination periods, the AE will be classified to the vaccination period. If the end date of the AE is missing, then the date of the last follow-up will be used for imputation.

Medication/Procedure

If a medication time is missing or partially missing and it cannot be determined whether it was taken prior or concomitantly or stopped prior to the first dose of Moderna mRNA-1273 vaccine

or REGN10933+REGN10987 (as applicable and whichever occurs first), it will be considered as concomitant medication/procedure by imputing the start time on the time of first dose of Moderna mRNA-1273 vaccine or REGN10933+REGN10987 (as applicable and whichever occurs first).

Potentially Clinically Significant Values

If a subject has a missing baseline value, this subject will be grouped in the category “normal/missing at baseline.”

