11.2. Criteria for Potentially Clinically Significant Values (PCSV)

Parameter	PCSV For Studies in healthy subjects only	Comments
Clinical chemistry		
ALT	>3 and \leq 5 ULN and baseline \leq 3 ULN >5 and \leq 10 ULN and baseline \leq 5 ULN >10 and \leq 20 ULN and baseline \leq 10 ULN >20 ULN and baseline \leq 20 ULN	Enzymes activities must be expressed in ULN, not in IU/L. Concept paper on DILI – FDA draft Guidance Oct 2007. Each category is calculated independently.
AST	>3 and \leq 5 ULN and baseline \leq 3 ULN >5 and \leq 10 ULN and baseline \leq 5 ULN >10 and \leq 20 ULN and baseline \leq 10 ULN >20 ULN and baseline \leq 20 ULN	Enzymes activities must be expressed in ULN, not in IU/L. Concept paper on DILI – FDA draft Guidance Oct 2007. Each category is calculated independently.
Alkaline Phosphatase	>1.5 ULN and baseline \leq 1.5 ULN	Enzymes activities must be expressed in ULN, not in IU/L. Concept paper on DILI – FDA draft Guidance Oct 2007. Internal DILI WG Oct 2008
Total Bilirubin	>1.5 and \leq 2 ULN and baseline \leq 1.5 ULN >2 ULN and baseline \leq 2.0 ULN	Must be expressed in ULN, not in μ mol/L or mg/L. Concept paper on DILI – FDA draft Guidance Oct 2008 Internal DILI WG Oct 2008
Conjugated bilirubin	>35% Total Bilirubin and TBILI > 1.5 ULN, and baseline Total Bilirubin \leq 35% or TBILI \leq 1.5 ULN	Conjugated bilirubin dosed on a case-by-case basis
ALT and Total Bilirubin	ALT > 3 ULN and TBILI > 2 ULN, and baseline ALT \leq 3 ULN or TBILI \leq 2 ULN	Concept paper on DILI – FDA draft Guidance Oct 2007 Internal DILI WG Oct 2008
CPK	>3 and \leq 10 ULN and baseline \leq 3ULN >10 ULN and baseline \leq 10ULN	FDA Feb 2005 Am J Cardio April 2006
Creatinine	\geq 150 μ mol/L (Adults) or \geq ULN (if ULN \geq 150 μ mol/L) and baseline < 150 μ mol/L or <ULN (if ULN \geq 150 μ mol/L) \geq 30% change from baseline \geq 100% change from baseline	Benichou C., 1994 3 independent criteria

Parameter	PCSV For Studies in healthy subjects only	Comments
Creatinine Clearance (Cockcroft's formula)	<15 ml/min and baseline \geq 15 ml/min (end stage renal impairment) \geq 15 - <30 ml/min and baseline \geq 30 ml/min (severe renal impairment) \geq 30 - < 60 ml/min and baseline \geq 60 ml/min (moderate renal impairment) \geq 60 - < 90 ml/min and baseline \geq 90 ml/min (mild renal impairment)	FDA draft guidance 2010 Four independent criteria
Uric Acid		

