Hyperuricemia:	>408 μ mol/L or >ULN (if ULN \geq 408 μ mol/L) and baseline \leq 408 μ mol/L or \leq ULN (if ULN \geq 408 μ mol/L)	Harrison- Principles of Internal Medicine 17 th Ed., 2008. Two independent criteria
Hypouricemia:	<120 μ mol/L or <LLN (if LLN \leq 120 μ mol/L) and baseline \geq 120 μ mol/L or \geq LLN (if LLN \leq 120 μ mol/L)	
Blood Urea Nitrogen	\geq 17 mmol/L or \geq ULN (if ULN \geq 17 mmol/L) and baseline <17 mmol/L or <ULN (if ULN \geq 17 mmol/L)	Two independent criteria
Chloride		
Hypochloremia:	<80 mmol/L or <LLN (if LLN \leq 80 mmol/L) and baseline \geq 80 mmol/L or \geq LLN (if LLN \leq 80 mmol/L)	Two independent criteria
Hyperchloremia:	>115 mmol/L or >ULN (if ULN \geq 115 mmol/L) and baseline \leq 115 mmol/L or \leq ULN (if ULN \geq 115 mmol/L)	
Sodium		
Hyponatremia:	\leq 129 mmol/L or \leq LLN (if LLN \leq 129 mmol/L) and baseline > 129 mmol/L or >LLN (if LLN \leq 129 mmol/L)	Two independent criteria
Hypernatremia:	\geq 160 mmol/L or \geq ULN (if ULN \geq 160 mmol/L) and baseline <160 mmol/L or <ULN (if ULN \geq 160 mmol/L)	
Potassium		
Hypokalemia	<3 mmol/L or <LLN (if LLN \leq 3 mmol/L) and baseline \geq 3 mmol/L or \geq LLN (if LLN \leq 3 mmol/L)	FDA Feb 2005. Two independent criteria
Hyperkalemia	\geq 5.5 mmol/L or \geq ULN (if ULN \geq 5.5 mmol/L) and baseline <5.5 mmol/L or <ULN (if ULN \geq 5.5 mmol/L)	

Parameter	PCSV For Studies in healthy subjects only	Comments
Total Cholesterol	≥ 7.74 mmol/L or \geq ULN (if ULN ≥ 7.74 mmol/L) and baseline < 7.74 mmol/L or $<$ ULN (if ULN ≥ 7.74 mmol/L)	Threshold for therapeutic intervention.
Triglycerides	≥ 4.6 mmol/L or \geq ULN (if ULN ≥ 4.6 mmol/L) and baseline < 4.6 mmol/L or $<$ ULN (if ULN ≥ 4.6 mmol/L)	Threshold for therapeutic intervention
Glucose		
Hypoglycaemia	≤ 3.9 mmol/L and $<$ LLN and baseline >3.9 mmol/L or \geq LLN	ADA Jan 2008.
Hyperglycaemia	≥ 11.1 mmol/L (unfasted); ≥ 7 mmol/L (fasted) and baseline < 11.1 mmol/L (unfasted); < 7 mmol/L (fasted)	
HbA1c	$>8\%$ and baseline $\leq 8\%$	
Albumin	≤ 25 g/L or \leq LLN (if LLN ≤ 25 g/L) and baseline >25 g/L or $>$ LLN (if LLN ≤ 25 g/L)	
CRP	>2 ULN or >10 mg/L (if ULN not provided) and baseline ≤ 2 ULN or ≤ 10 mg/L (if ULN not provided)	FDA Sept 2005
Hematology		

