WBC	<3.0 Giga/L or $<$ LLN (if LLN ≤ 3.0 Giga/L) and baseline ≥ 3.0 Giga/L or \geq LLN (if LLN ≤ 3.0 Giga/L) (Non-Black); <2.0 Giga/L or $<$ LLN (if LLN ≤ 2.0 Giga/L) and baseline ≥ 2.0 Giga/L or \geq LLN (if LLN ≤ 2.0 Giga/L) (Black) ≥ 16.0 Giga/L or \geq ULN (if ULN ≥ 16.0 Giga/L) and baseline < 16 Giga/L or $<$ ULN (if ULN ≥ 16.0 Giga/L)	Increase in WBC: not relevant.
Lymphocytes	>4.0 Giga/L or $>$ ULN (if ULN ≥ 4.0 Giga/L) and baseline ≤ 4.0 Giga/L or \leq ULN (if ULN ≥ 4.0 Giga/L)	
Neutrophils	<1.5 Giga/L or $<$ LLN (if LLN ≤ 1.5 Giga/L) and baseline ≥ 1.5 Giga/L or \geq LLN (if LLN ≤ 1.5 Giga/L) (Non-Black); <1.0 Giga/L or $<$ LLN (if LLN ≤ 1.0 Giga/L) and baseline ≥ 1.0 Giga/L or \geq LLN (if LLN ≤ 1.0 Giga/L) (Black)	International Consensus meeting on drug-induced blood cytopenias, 1991.

Parameter	PCSV For Studies in healthy subjects only	Comments
Monocytes	>0.7 Giga/L or >ULN (if $ULN \geq 0.7$ Giga/L) and baseline ≤ 0.7 Giga/L or \leq ULN (if $ULN \geq 0.7$ Giga/L)	
Basophils	>0.1 Giga/L or >ULN (if $ULN \geq 0.1$ Giga/L) and baseline ≤ 0.1 Giga/L or \leq ULN (if $ULN \geq 0.1$ Giga/L)	
Eosinophils	>0.5 Giga/L or >ULN (if $ULN \geq 0.5$ Giga/L) and baseline ≤ 0.5 Giga/L or \leq ULN (if $ULN \geq 0.5$ Giga/L)	Harrison- Principles of Internal Medicine 17 th Ed., 2008.
Hemoglobin	
≤ 115 g/L or \leqLLN (if $LLN \leq 115$ g/L) and baseline > 115 g/L or $>$LLN (if $LLN \leq 115$ g/L) for male; ≤ 95 g/L or \leqLLN (if $LLN \leq 95$ g/L) and baseline > 95 g/L or $>$LLN (if $LLN \leq 95$ g/L) for Female.
 
≥ 185 g/L or \geqULN (if $ULN \geq 185$ g/L) and baseline < 185 g/L or $<$ULN (if $ULN \geq 185$ g/L) for Male; ≥ 165 g/L or \geqULN (if $ULN \geq 165$ g/L) and baseline < 165 g/L or $<$ULN (if $ULN \geq 165$ g/L) for Female
 
Decrease from Baseline ≥ 20 g/L
	Three criteria are independent.
Hematocrit	
≤ 0.37 v/v or \leqLLN (if $LLN \leq 0.37$ v/v) and baseline > 0.37 v/v or $>$LLN (if $LLN \leq 0.37$ v/v) for Male; ≤ 0.32 v/v or \leqLLN (if $LLN \leq 0.32$ v/v) and baseline > 0.32 v/v or $>$LLN (if $LLN \leq 0.32$ v/v) for Female
 
≥ 0.55 v/v or \geqULN (if $ULN \geq 0.55$ v/v) and baseline < 0.55 v/v or $<$ULN (if $ULN \geq 0.55$ v/v) for Male; ≥ 0.5 v/v or \geqULN (if $ULN \geq 0.5$ v/v) and baseline < 0.5 v/v or $<$ULN (if $ULN \geq 0.5$ v/v) for Female
	Two Criteria are independent
RBC	≥ 6 Tera/L or \geq ULN (if $ULN \geq 6$ Tera/L) and baseline < 6 Tera/L or $<$ ULN (if $ULN \geq 6$ Tera/L)	

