Parameter	PCSV For Studies in healthy subjects only	Comments
Platelets	<100 Giga/L or <LLN (if LLN≤100 Giga/L) and baseline ≥100 Giga/L or ≥LLN (if LLN≤100 Giga/L) ≥700 Giga/L or ≥ULN (if ULN≥700 Giga/L) and baseline < 700 Giga/L or <ULN (if ULN≥700 Giga/L)	International Consensus meeting on drug-induced blood cytopenias, 1991. Two independent criteria
Vital signs		
HR	<45 bpm and decrease from baseline ≥20 bpm ≥120 bpm and increase from baseline≥20 bpm	To be applied for all positions except STANDING
SBP	≤95 mmHg and decrease from baseline ≥20mmHg ≥160 mmHg and increase from baseline ≥20 mmHg	To be applied for all positions except STANDING
DBP	≤45 mmHg and decrease from baseline ≥10 mmHg ≥110 mmHg and increase from baseline ≥10 mmHg	To be applied for all positions except STANDING
Weight	≥ 5% increase from baseline ≥5% decrease from baseline	FDA Feb 2007

Signature Page for VV-RIM-00211857 v1.0

Approval/eSignature	 -2022 18:02:27 GMT+0000
---------------------	---

Approval/eSignature	 22 18:34:27 GMT+0000
---------------------	--

Approval/eSignature	 -2022 18:44:19 GMT+0000
---------------------	---

Approval/eSignature	 00
---------------------	--

Approval/eSignature	 00
---------------------	--

Approval/eSignature	 00
---------------------	--

Signature Page for VV-RIM-00211857 v1.0 Approved

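### For about 50 of 53 laboratory PCSV criteria, the all-subjects table repeats the numerator of the normal-or-missing-baseline table, because SAP 11.2 already builds in the baseline condition

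*SAP*

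**What the plan says.** SAP 5.8.2 asks for the number and percentage of subjects with a PCSV at any time after randomization, for each laboratory test, "for all subjects and separately for subjects in whom the PCSV criterion was normal or missing at baseline". Protocol 11.4.6.2 asks for the same two summaries and does not define a PCSV.

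The definitions come from the SAP. Section 4.6.3 states that PCSV "ranges will be applied to the laboratory test values as applicable (see PCSV criteria in Appendix 11.2"). Most laboratory entries in that appendix join a post-baseline threshold to a condition on the baseline value:

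- Alkaline phosphatase: ">1.5 ULN and baseline \leq 1.5 ULN".
- High potassium, after the post-baseline limit: "and baseline <5.5 mmol/L or <ULN (if ULN \geq 5.5 mmol/L").
- Low platelets, after the post-baseline limit: "and baseline ≥100 Giga/L or ≥LLN (if LLN≤100 Giga/L").

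Some entries are tiered, such as the second ALT tier: ">5 and \leq 10 ULN and baseline \leq 5 ULN". Three entries depend on change alone: the two creatinine percentage changes (30% and 100%) and, for haemoglobin, "Decrease from Baseline ≥ 20 g/L".

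On missing baselines SAP 6.3 says: "If a subject has a missing baseline value, this subject will be grouped in the category" normal/missing. The same section uses eosinophils to illustrate a missing upper limit of normal (ULN). There the PCSV is a value above 0.5 Giga/L, or above the ULN where that is at least 0.5, with no baseline condition. The eosinophil row in 11.2 adds one.

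**The concern.** Two tables are useful if they count different things: one every post-dose value beyond the limit, the other only values that were not there at baseline. If the definition already contains the baseline condition, the first table has the same cases as the second over a larger denominator. Subjects beyond the limit at baseline then count as non-events in a table labelled as covering everyone.

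Such subjects can be enrolled. Protocol 7.2.1 admits stable chronic conditions and ages up to 90, Protocol 7.2 aims for 30% to 50% aged 65 or over at each site, and Protocol 7.2.2 sets no haematology or chemistry limit. At stake is how complete one descriptive safety table is.

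**Working it through.** The plan states no figure on this point, so there is none to reproduce. The check counts the criteria, compares the two numerators, and shows the size under stated assumptions.

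**1. Count of laboratory criteria in SAP 11.2** (vital signs and weight left out; each threshold, tier or change rule counted once)

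| Type | Criteria |
|---|---|
| Contains a baseline condition | 50 |
| Change only (creatinine 2, haemoglobin 1) | 3 |
| Total, over 30 parameters | 53 |

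50/53 = 94%. Splitting rows differently would move the count slightly, hence *about* 50.

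**2. The two numerators.** For one criterion, let T mean that the post-baseline value is beyond the threshold, and B that the baseline is not.

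- All-subjects cases under 11.2: T and B, plus any missing-baseline cases.
- Restricted-table cases: the same subjects, because the subset is B or missing.

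Missing baselines do not separate the tables, since those subjects belong to the subset and are judged alike in both. The identity takes *normal* to mean that the criterion is not met at baseline, which is how 5.8.2 words it. If *normal* meant within the laboratory reference range, the subset would be narrower and the numerators could differ.

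An illustration with invented potassium-like values (1,000 subjects, threshold 5.5 mmol/L) gives 110/1000 for all subjects and 110/968 for the subset. The threshold alone gives 136/1000.

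**3. Which criteria can count worsening from a baseline already at PCSV level**

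- Tiered or composite criteria that can: ALT 3, AST 3, total bilirubin 1, conjugated bilirubin 1, ALT with bilirubin 1, CPK 1, creatinine clearance 3. Total 13.
- Change-only criteria: 3.
- Can: 13 + 3 = 16 of 53 (30%).
- Cannot: 53 − 16 = 37 of 53 (70%). For 21 of 30 parameters no criterion can; these include platelets, neutrophils, potassium, albumin and alkaline phosphatase.

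The ALT rules show where the line falls, in multiples of ULN: 2 to 4, 4 to 6 and 6 to 12 are counted; 4 to 4.8, 6 to 9 and 21 to 30 are not.

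**4. Size under assumptions.** Let b be the fraction beyond a given threshold at baseline that stays beyond it, and let 3% of the rest cross it. Both are assumptions. The planned enrolment of 286 is from Protocol 7.1.

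- All-subjects rate as written: (1 − b) × 0.03
- All-subjects rate with threshold alone: (1 − b) × 0.03 + b
- Subjects left out: 286 × b

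| b | As written | Threshold alone | Left out |
|---|---|---|---|
| 1% | 2.97% | 3.97% | 2.9 |
| 3% | 2.91% | 5.91% | 8.6 |
| 5% | 2.85% | 7.85% | 14.3 |
| 10% | 2.70% | 12.70% | 28.6 |

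The restricted table would show 3% in every row. The left-out column measures persistence of a baseline abnormality, not deterioration.

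**5. Eosinophils.** Take a laboratory ULN of 0.5 Giga/L or below and a baseline of 0.6. A post-dose value above 0.5 is a PCSV by the wording in 6.3 and not by the row in 11.2, so two programmers could produce different all-subjects counts.

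**The case against.** The strongest reply is that this is redundancy in a descriptive table. Neither document says that the all-subjects table must show every value regardless of baseline, and a sponsor may prefer to count only emergent values. Dropping the clause would also count stable or improving subjects: ALT falling from 6 to 4 times ULN would become an event in the tier above 3 and up to 5. That is a real cost of the fix. It does not explain why two tables with the same cases are planned.

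The eosinophil wording in 6.3 may be shorthand, since its subject is a missing ULN. It still differs from 11.2 and needs aligning.

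A reader might infer more than the documents support:

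- **That the baseline must be normal.** The clause only requires a baseline not beyond the PCSV threshold. ALT rising from 2 to 4 times ULN is counted in both tables.
- **That a subject beyond a threshold at baseline can never be a case.** The tiers and change criteria above show otherwise for several tests.
- **That a given fall is certain to be missed.** Platelets falling from 95 to 20 Giga/L would be counted if the laboratory's lower limit were 95 or less. The neutrophil limits also depend on race. The documents do not give the laboratory limits.
- **That deterioration is hidden.** SAP 5.8.2 tabulates change from baseline for every test. Protocol 9.2.5 requires investigator review of all values and repeat of significantly abnormal ones, and Protocol 10.1.1 covers adverse event reporting. Change summaries are group statistics, however, and shift tables are optional; a normal/abnormal shift would not separate a stable abnormality from a deeper one.

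Exclusions 8 and 9 in Protocol 7.2.2 remove significant disease at the investigator's judgment, which makes the upper end of the assumed range less likely.

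**Conclusion.** The point holds in a limited form. For about 50 of 53 laboratory criteria the two planned tables share a numerator, and subjects already beyond the threshold at baseline are non-events in the all-subjects table. For 37 of 53 criteria, further worsening from such a baseline is counted in neither table. SAP 6.3 and 11.2 disagree for eosinophils.

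This rests on reading *normal* as criterion not met at baseline. The number of subjects affected is unknown. The range of about 3 to 29 of 286 per test depends wholly on assumed persistence of 1% to 10%, and it would be wrong to read it as missed deteriorations. The primary endpoint is untouched; the effect is confined to descriptive safety tables. This is a minor point, worth correcting because it is cheap.

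**What to change.** In SAP 5.8.2 and 11.2:

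- For the all-subjects table, apply the post-baseline threshold without the baseline clause. Leave the creatinine percentage-change and haemoglobin-decrease criteria as they are.
- For the normal-or-missing table, keep the clause, and state that *normal* means the criterion is not met at baseline.
- Label the all-subjects table as regardless of baseline, and present it beside the restricted one.
- In 6.3, align the eosinophil example with 11.2.

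The cost is a wording change and one programming flag; the data are already collected. The all-subjects percentages will rise, in the assumed cases from 2.97% to 3.97% at b = 1% and from 2.70% to 12.70% at b = 10%. The table will then mix stable and improving pre-existing abnormalities with new ones, so the restricted table remains the one to read for emergent values.

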5.8.3. Vital Signs

Vital signs (temperature, blood pressure, heart rate, and respiratory rate) will be tabulated by baseline and change from baseline to each scheduled assessment time with descriptive statistics. Graphs of mean (+/- SE) value may be provided.

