8.5. Method of Enrollment and Treatment Assignment

Site-managed assignment. At screening, eligible subjects will be assigned to an enrollment wave. The enrollment waves are intended to avoid or minimize the potential for unused doses of Moderna mRNA-1273 COVID-19 vaccine (refer to Section 3.2.1 for additional rationale). Every effort should be made by sites to avoid unused doses of vaccine.

Sites will manage the placement of subjects into each wave. Every effort should be made by the site to ensure balance of age (<65 years and \geq 65 years) within each of the enrollment waves.

Randomization. At baseline (day 1), subjects will be randomized to the corresponding study arms in each wave as described in [Table 2](#).

Randomization will be performed according to a computer-generated randomization scheme provided by an interactive web response system (IWRS) to a designated study pharmacist or a qualified designee.

Randomization will be stratified by age (<65 years versus \geq 65 years).

Table 2: Study Treatment Assignment

Study Arm	Randomization Ratio	Targeted Enrollment	Co-administered REGN10933+REGN10987 Combination Therapy	Moderna mRNA-1273 Vaccine*
Enrollment Wave 1				
1	2	30	1200 mg (600 mg of each mAb) IV on day 1	On day 15 and day 43
2	2	30	300 mg (150 mg of each mAb) IV on day 1	On day 15 and day 43
3	2	30	150 mg (75 mg of each mAb) IV on day 1	On day 15 and day 43
6a	1	15	None	On day 15 and day 43
Enrollment Wave 2				
4	2	30	1200 mg (600 mg of each mAb) SC on day 1	On day 1 and day 29
5	2	30	600 mg (300 mg of each mAb) SC on day 1	On day 1 and day 29
6b	1	15	None	On day 1 and day 29
Enrollment Wave 3				
7	15	30	48 mg (24 mg of each mAb) IV on day 1	On day 15 and day 43
8	15	30	12 mg (6 mg of each mAb) IV on day 1	On day 15 and day 43
6c	4	8	None	On day 15 and day 43
Enrollment Wave 4				
9	15	30	1200 mg (600 mg of each mAb) IV on day 7	On day 1 and day 29
6d	4	8	None	On day 1 and day 29

*Moderna mRNA-1273 vaccine will be administered as described on the EUA Fact Sheet ([Moderna COVID-19 Vaccine \[HCP Fact Sheet\], 2022](#)).

mAb=monoclonal antibody; SC=subcutaneous; IV=intravenous.

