7. Note that not all subjects will receive study drug at randomization. Refer to Section 8.5 and Figure 1 for more information.

Study arms 4 and 5: Subjects assigned to study arms 4 and 5 will receive both the study drug and vaccine on day 1. The study drug will be administered first, followed by the vaccine. There must be a minimum of 2 hours waiting period between administration of the study drug and subsequent vaccine administration. Approximately 24 hours after completion of the study drug and vaccine administration on day 1, subjects will be followed up by telephone for safety. Subjects should be monitored for at least 1 hour after study drug or vaccine administration.

Study arms 6a, 6b, 6c, and 6d only: Subjects assigned to one of these study arms will not receive study drug. These subjects will receive the vaccine only. These subjects should be monitored for at least 30 minutes after vaccine administration.

Refer to Section 9.2.2 for additional information concerning administration and monitoring requirements following study drug and/or vaccine administration.

8. Serology characterization assays will be used to assess antibodies against various SARS-CoV-2 antigens including: S protein, RBD, S1, and N protein. Refer to Section 9.2.3.1, Section 9.2.3.2, and Section 9.2.3.3 for more information on procedures and assays related to vaccine response assessment.
9. Vital signs, including temperature, blood pressure, heart rate, and respiratory rate will be collected prior to and 30 minutes following each administration of the study drug or vaccine primary series (first and second dose) as described in Section 9.2.4.1.
10. Actual dosing time and drug concentration sample collection times will be recorded.

Study arms 1, 2, 3, 7, 8, and 9 (receiving IV infusion of study drug): At the indicated visit, blood for assessment of drug concentration in serum will be taken prior to dosing and within 60 minutes after the end of infusion (EOI). The EOI sample should be collected from the arm contralateral to that used for IV infusion. If not medically feasible, the EOI sample can be drawn from the same arm, but not from the infusion catheter.

Study arms 4 and 5 (receiving SC injection of study drug): At the screening/baseline visit, blood for assessment of drug concentration in serum will be taken prior to dosing. The post-dose blood collection should occur at least 1 hour after study drug administration.

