6.1. Definition of Baseline

Unless otherwise specified, the baseline assessment for all measurements will be the latest available valid measurement taken prior to the administration of the first dose of Moderna mRNA-1273 vaccine or REGN10933+REGN10987 (as applicable and whichever occurs first).

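### In waves 1 and 3, the vital-sign change after vaccine dose 1 spans about 14 days in the drug arms but about 30 minutes in their concurrent controls; a same-visit change should be added.

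*SAP*

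**What the plan says.** **Collection.** Footnote 9 to the Schedules of Events (Protocol 9.1.1) states that vital signs "will be collected prior to and 30 minutes following each administration of the study drug or vaccine primary series". Protocol 9.2.4.1 repeats this. Each dosing visit thus yields a pre-dose and a post-dose reading in every arm.

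**Summary.** SAP 5.8.3 plans that vital signs "will be tabulated by baseline and change from baseline to each scheduled assessment time with descriptive statistics". Protocol 11.4.6.2 says the same in substance. Neither mentions a change within a visit.

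**Baseline.** SAP 6.1 sets the default: "Unless otherwise specified, the baseline assessment for all measurements will be the latest available valid measurement taken prior to the administration". The anchor is whichever product a subject is given earliest, study drug or vaccine. SAP 5.7 sets a different baseline, anchored on the first vaccine dose, but only for the efficacy variables.

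**Dosing days.** In Protocol 8.5, Table 2, all arms of waves 1 and 3 receive vaccine "On day 15 and day 43". Arms 1, 2, 3, 7 and 8 also receive study drug on day 1; 6a and 6c receive none.

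**Flagging.** SAP 4.6.4 applies PCSV ranges to vital signs. In SAP 11.2 the heart rate and blood pressure criteria pair an absolute limit with a change from baseline, for example "≤95 mmHg and decrease from baseline ≥20mmHg" for systolic pressure.

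**The concern.** A reading 30 minutes after a dose is most informative against the reading taken just before that dose. The plan collects this pair but does not use it as one.

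Within waves 1 and 3 the fixed baseline also falls at a different point for drug arms and controls, because only the drug arms receive anything on day 1. At vaccine dose 1 the same row of the table then holds two quantities. In the controls it is a short-term response to the vaccine. In the drug arms it is that response plus whatever moved between day 1 and day 15.

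Safety and tolerability of the two products given in close succession is a secondary objective (Protocol 2.2, SAP 1.2.2), and this row is one of the places where a reader would look for it.

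**Working it through.** **Plan's own interval.** Protocol 6.1 gives 28 days between vaccine doses. Table 2 reproduces it: 43 − 15 = 28 and 29 − 1 = 28.

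**Age of the baseline at the post-dose reading.** Baseline day = the earlier of the study drug day and the vaccine dose 1 day. Age = dosing day − baseline day. Days come from Protocol Table 2; the visit window at the day 15 and day 43 visits is −1 to +3 days (Protocol Table 3).

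| Arms | Baseline day | Vaccine dose 1 | Vaccine dose 2 | Study drug dose |
|---|---|---|---|---|
| 1, 2, 3, 7, 8 | 1 | 15 − 1 = 14 days (13 to 17) | 43 − 1 = 42 days (41 to 45) | same visit |
| 6a, 6c | 15 | about 30 min | 43 − 15 = 28 days | none |
| 4, 5 | 1 | same day, at least 2 h + 30 min | 29 − 1 = 28 days | same visit |
| 6b | 1 | about 30 min | 28 days | none |
| 9 | 1 | about 30 min | 28 days | 7 − 1 = 6 days |
| 6d | 1 | about 30 min | 28 days | none |

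The 2 hours for arms 4 and 5 is the minimum wait between study drug and vaccine in footnote 7. The 14-day contrast affects 5 of 8 drug arms, 5 × 30 = 150 of 8 × 30 = 240 planned study drug subjects, in two of four waves. All four control arms have an interval of about 30 minutes at dose 1, so pooling the controls would not remove it.

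**Effect on spread.** With a common SD σ and correlation ρ between two readings, SD of change = σ√(2(1 − ρ)). The ratio of drug arm to control is √((1 − ρ at 14 days)/(1 − ρ within a visit)), and σ cancels. The documents give no correlations; the ranges below are assumptions.

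| ρ within a visit | ρ at 14 days | Ratio of SDs |
|---|---|---|
| 0.8 | 0.7 | √(0.3/0.2) = 1.22 |
| 0.8 | 0.5 | √(0.5/0.2) = 1.58 |
| 0.9 | 0.7 | √(0.3/0.1) = 1.73 |
| 0.9 | 0.5 | √(0.5/0.1) = 2.24 |

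**Effect on flags.** This is an illustration for systolic pressure, assuming SD 12 mmHg, correlation 0.60 over 14 days, joint normality and no mean change. The SD of change is 12√(2 × 0.40) = 10.73 mmHg, and a change of at least 20 mmHg in either direction has probability 6.2%. A flag also needs a value of at most 95 or at least 160 mmHg. With a mean of 120 to 130 mmHg the joint probability falls to about 0.2% to 0.4%, or 0.3 to 0.6 expected chance flags among 150 subjects at dose 1. The corresponding probability at correlation 0.85 within a visit is about 0.01%. With SD 15 and mean 125 the expected number over 14 days rises to about 1.6.

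**The case against.** A fixed pre-treatment baseline is a coherent choice in a study with no hypothesis testing (Protocol 11.1). It also shows any sustained shift after study drug, which a same-visit reference would hide. For study drug given on day 1, the planned reference already is the same-visit reading in seven of eight drug arms. Vital-sign change is not an endpoint. Acute tolerability is covered mainly by the reaction endpoints, the AESIs and the adverse event tables by period. This all stands, and it makes the point a small one.

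It can also be said that a reader may subtract the pre-dose mean from the post-dose mean. That holds only if both are shown. SAP 6.4 groups assessments by eCRF visit label, and SAP 5.8.3 does not say whether the two readings of a visit are displayed separately. Even then, subtraction gives the mean within-visit change (given complete pairs) but not its SD.

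Three stronger readings are tempting, and the documents do not support them:

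- **That every drug arm is out of step with its control.** Arms 4 and 5 have a same-day baseline, and arm 9 matches 6d at dose 1. At dose 2 the contrast is 42 v 28 days, not 42 days v 30 minutes.
- **That PCSV counts will be distorted between arms.** SAP 5.8.2 plans PCSV counts for laboratory tests. SAP 5.8.3 plans none for vital signs, and the absolute limits would keep chance flags rare. The 6.2% above is not a flag rate.
- **That day-to-day variation hides the acute change.** No acute effect size is given, so this cannot be judged.

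**Conclusion.** The mismatch is real but minor. It follows from SAP 5.8.3 read with SAP 6.1, and it is limited to arms 1, 2, 3, 7 and 8 against 6a and 6c: about 14 days v about 30 minutes at vaccine dose 1, and 42 v 28 days at dose 2. Separately, arm 9's post-infusion reading on day 7 is referred to a value 6 days old, although a pre-dose reading is scheduled at that visit.

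The consequence is a noisier change in the affected drug arms and a mean that carries any drift between day 1 and day 15, which the control mean does not. The intervals are nominal; if the day 1 pre-dose value is missing, the baseline moves back to screening. The 1.2- to 2.2-fold ratio of SDs rests wholly on assumed correlations and equal SDs. Its direction needs only that readings 30 minutes apart agree better than readings 14 days apart. No primary result or sample size figure is affected, and the study baseline need not be abandoned.

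**What to change.** In SAP 5.8.3:

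- Tabulate the pre-dose and post-dose readings of each dosing visit as separate rows.
- For every study drug and primary-series vaccine administration, in all arms, add the change from the same-visit pre-dose reading to the 30-minute post-dose reading.
- Keep the change from study baseline alongside it, so that sustained shifts remain visible.
- If vital-sign PCSVs are tabulated by arm, also show the change component for post-dose values against the same-visit pre-dose reading.

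The added change then spans about 30 minutes in every arm at every dose. The cost is one derived variable and one extra table, with no new data collection.
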